4.6. STUDY PROCEDURES

We will conduct an RCT pilot trial of the adapted couple-based intervention. 66 couples will be randomized into two arms – 33 couples into the intervention arm and 33 couples into standard of care (SOC). SOC consists of an appointment with an AIDS Center nurse at baseline and three and six months later. Under current SOC in Almaty, no behavioral intervention is provided. Participants obtain prescription refills and give blood for viral load and CD4 tests once every 6 months. Participants receive viral load and CD4 test results only by request, and adherence is generally not assessed. We anticipate the intervention will consist of 3 sessions over the course of one month. Participants in both arms will be assessed at 4 time points: baseline “pre-intervention”, immediately post-intervention (IPI), 3-month follow-up, and 6-month follow-up. **Figure 2** illustrates participant flow through the study.

4.6.1. Baseline Visit (for all participants)

Baseline visits will be conducted remotely by phone/video call using video call platforms that are commonly used in Kazakhstan and available on participant phones or in-person in GHRCCA’s field office. Prior to remote visits, an RA will mail a baseline kit to participants containing an electronic monitoring device (EMD), study phone, and materials to self-collect hair and urine samples. The following procedures/assessments will be performed at the baseline visit:

1. The RA will complete the **Locator Information Form**;
2. The RA will send the **Baseline Assessment** through Qualtrics;
3. The RA will set-up **electronic monitoring device (EMD)** and phone app with participants. The RA will instruct the participants on proper EMD use and conduct an EMD test to confirm that the device is working properly and is connected with the data server;
4. To ensure equal distribution between study arms by the sex of the “index case” and those on tenofovir-based regimens, a randomization list will be generated. The dyad will be **randomized** to an intervention arm; If the dyad is randomized to Standard of Care, they will be sent informational materials. If they are randomized to the intervention, they will be scheduled an intervention appointment with an intervention facilitator.
5. Participants will self-collect urine samples and hair samples to measure biological levels of medication adherence. These samples will be mailed to GHRCCA staff.

4.6.2. Intervention Visits (for participants in the intervention arm)

Intervention sessions will be conducted by phone/video call or in-person in the psychologist’s office (post-COVID) at the AIDS Center. The following procedures/assessments will be performed at the intervention visits:

1. The intervention facilitator will verify the participants by name.
2. The intervention facilitator will request **informed consent** to audiotape the intervention session. If both members of the dyad consent, the intervention facilitator will mark that consent was given and the audiorecorder will be turned on.
3. The facilitator will explain the purpose and activities of the day’s session. S/he will go over the EMD adherence data of HIV-positive participants and discuss adherence patterns and challenges with the dyad.
4. The facilitator will conduct the day’s session with the dyad.

All intervention sessions (3 sessions per couple) must be completed within two months of when the first intervention session is conducted.

4.6.3. Immediately Post-Intervention (IPI) Visit (for all participants)

The IPI will be conducted by phone/video call or in-person in GHRCCA’s field office (post-COVID). Prior to the visit, an RA will mail an IPI kit to participants containing materials to self-collect hair and urine samples. For in-person visits, participants will self-collect samples at the GHRCCA field office. The following procedures/assessments will be performed at the IPI visit:

1. The RA will verify the participants by the name on the record and update the **Locator Information Form**;
2. The RA will send the **IPI Assessment** through Qualtrics;
3. The RA will conduct an **EMD** test and will check in with the participant regarding EMD uses and resolve any issues;
4. Participants will self-collect urine samples and hair samples to measure biological levels of medication adherence. These samples will be mailed to GHRCCA staff.
5. At the participant’s next regular AIDS Center visit, the nurse will obtain an additional **blood sample** to conduct dried blood spot sampling and measure levels of medication in the body

4.6.4. 3-month and 6-month Follow-Up Visits (for all participants)

Three- and six-month Follow-Up Visits will be conducted by phone/video call or in-person in GHRCCA’s field office (post-COVID). The following procedures/assessments will be performed at the 3- and 6-month follow-up visits:

1. The RA will verify the participants by the name on the record and update the **Locator Information Form**;
2. The RA will send the **3- or 6-month follow-up assessment** through Qualtrics;
3. At the **3-month** follow-up, the RA will conduct an **EMD** test and will check in with the participant regarding EMD uses and resolve any issues. At the **6-month** follow-up, the participant will mail the **EMD** back to the RA.
4. After the **6-month** follow-up, the RA will administer the Exit Interview;

4.6.5. Pilot study assessments. Participants in both arms will receive the same schedule of assessments. There will be four main repeated assessment occasions: baseline “pre-intervention”, immediately post-intervention (IPI), 3-month and 6-month follow-up. The primary adherence outcome will be proportion of prescribed doses taken as measured by EMD. Study assessments will be delivered remotely through Qualtrics.

4.6.6. Electronic Monitoring Device (EMD) Data. We will continuously monitor EMD device openings. The EMD sends a signal to a secure website via cellular data networks whenever the device is opened as a proxy for ART adherence. If connection or SIM card problems prevent real-time monitoring, records and diagnostics are stored (up to 1 year) and uploaded to the server when a connection is re-established. The device can store a 30-day supply of medication. EMD-measured adherence will be operationalized as percentage of days/doses for which a device-opening signal was received in the past month. EMDs will be given to participants in both arms. Pills will be deposited into the EMD device, which will record every time the device is opened. EMD data will allow patients to see objective feedback of their adherence patterns, which could help them improve their medication adherence.

At the conclusion of the baseline visit, the RA will mail the participant an EMD device with instructions on how to fill the device, open it for dosing, and pair it with the app. The RA will call the participant to assist with troubleshooting and confirm that the EMD device is properly set up, that it is recognized by the EMD server, and that device openings are being recorded properly (date and time). If 7 days pass and the device is not seen at all on the server, the RA will call the participant to see if there are any device problems. At each study visit, the RA will ask if the participant is having any problems using the EMD.

4.6.7. Weekly app assessments on a mobile phone. Based on GHRCCA’s previous studies, we anticipate that participants will own a smart phone. We will pay for all participants’ data plans during the course of the study. Weekly assessment data will be collected once a week throughout the course of the study through an app which will be installed on participants’ phones. Assessment items will focus on drug use in the past week, adherence to ART, social support, and relationship satisfaction.

4.6.8. Biological Sample Collection. DBS samples for TDF-DP assay. Dried blood spot (DBS) samples will be collected from HIV-positive participants at their regular AIDS Center visit to assess feasibility and acceptability of the biological collection process and measure biological levels of medication. A nurse will collect DBS samples by venipuncture, using a pipette to spot blood directly onto Whatman 903 ProteinSaver cards. The cards will be air-dried, individually packaged in a plastic bag with desiccant, and transferred to a -20 to -80°C freezer for storage. Only samples of participants on tenofovir-based regimens will be shipped to the US, allowing us to assess the feasibility and acceptability of storage and shipment processes.

Hair samples for ART levels. Participants will self-collect hair samples and mail them to GHRCCA staff. To collect hair samples, participants will need to cut a small thatch of hair (~50 strands of hair) close to the scalp from a bottom layer of their hair. Hair should be placed in a piece of tinfoil and inside a Ziploc bag labeled with their study ID. Participants will ship samples to GHRCCA staff, who will then batch ship samples to the US for testing, allowing us to assess biological measures of ART adherence over the past several weeks.

Urine samples for point-of-care ART urine tests. Participants will self-collect urine samples and mail them to GHRCCA staff. To collect urine samples, participants will need to pee in a cup labeled with their study ID. Upon receipt of urine samples, GHRCCA staff will conduct point-of-care urine tests according to manufacturer protocols. This will allow us to assess biological measures of ART adherence over the previous 48 hours.

4.6.8.1. Assays. DBS assays. All DBS samples from participants taking tenofovir-based regimens will be batch-shipped to a lab in the United States for assay after all participants complete the intervention period. DBS samples will be shipped to the University of Colorado on dry ice for analysis using [name] current validated assay for TDF-DP.²² Hair assays. All hair samples from HIV-positive participants will be batch-shipped

to a lab in the United States for assay after all participants complete hair sampling. Hair samples will be shipped to the University of California-San Francisco for analysis using [name] current validated assay for hair samples. Urine assays. All urine samples will be tested by GHRCCA research staff using UrSure's validated assay for urine samples.

4.6.8.2. Biohazard Containment. As the transmission of HIV and other blood-borne pathogens can occur through contact with contaminated needles, blood, and blood products, appropriate blood and secretion precautions will be employed by all personnel in the drawing of blood and shipping and handling of all specimens for this study, as currently recommended by the Centers for Disease Control and Prevention and the World Health Organization. The Almaty AIDS Center has extensive experience and authorization for the handling and containment of hazardous materials. AIDS Center staff complete regular safety training on exposure control, managing hazardous materials, and safe biospecimen collection, storage, and disposal. The University of Colorado Antiretroviral Laboratory has biosafety authorization for handling and containment of hazardous materials. Training is required within 6 months of hire and on an annual basis thereafter. Training includes Hazardous Chemical Waste Management and Bloodborne Pathogens Exposure Control Training for Research. Documentation is maintained in laboratory personnel records.

4.6.9. Medical Record Data. Almaty AIDS Center staff will provide research staff with limited electronic medical record data in order to determine participant eligibility and assess intervention outcomes. Electronic medical record data will be de-identified and assigned a unique study ID before they are provided to research staff. Almaty AIDS Center's Electronic HIV Case Management System (EHCMS) is a government-approved computer system for the collection, storage, transfer and analysis of epidemiological, laboratory and clinical data on all registered cases of HIV infection in Kazakhstan. Within this system, a file is created for each client who registers for treatment at the AIDS Center. All visits, tests, results and treatment information for each client are regularly entered by staff from the epidemiology and treatment department. Data extraction from this database will be done by AIDS Center staff who already have access to it. Data provided to GHRCCA research staff will be stripped of all PII identifiers. Data will be linked to participant study data through a unique study ID. Data extracted will include 1) HIV status, 2) PWID status, 3) Current ART regimen and ART regimens over the past year, 4) Length of time on ART, and 5) Viral load test results over the past year. Coded data will be entered into a password-protected file and sent via encryption to GHRCCA staff.

4.6.10. Quality control/intervention fidelity. To determine the extent to which the intervention is implemented as planned, we will use monitoring systems as in previous studies.^{35,43,47,48} We will assess participant attendance, protocol adherence, and the integrity of implementation. We will audiotape all intervention sessions where participant consent is provided for quality assurance and supervision purposes. We will randomly select and review 20% of sessions in order to assess quality control and implementation fidelity.

4.6.11. Safety, Acceptability, Feasibility, Retention and Implementation Data. Intervention safety will be assessed through adverse event reporting by study and clinic staff and an exit interview asking about any negative experiences during the intervention. We will assess acceptability and feasibility of the adapted intervention and biological testing. Both partners will be assessed at the end of each intervention session on satisfaction and obstacles to participation. A brief survey will ask about participants' experiences with biological sample collection. We will track the number of participants retained in the study. For those who drop out, we will attempt to contact them to determine the reason. Staff will be asked questions about intervention delivery, specimen collection and challenges and facilitators of implementation.

4.6.12. Sample size and power considerations for the pilot RCT. We can estimate power for this study based on previous studies.^{33,35} Based on Project Renaissance attrition rates,³³ we anticipate there will be no more than 10% attrition throughout the study. Power analyses were conducted with G*Power⁴⁹ (v3.1.0) using a repeated measures within-between ANOVA approach and $\alpha=.05$. With 30 dyads per arm, we would have 80% power to detect a medium effect size ($f=.15$). Thus, we will recruit 66 couples and aim to have 60 for analysis.

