5.1. Quality Control and Quality Assurance. In collecting the vast majority of the study data electronically, we will be able to closely monitor the quality and completeness of the data in near-real time and strive to correct any mistakes before they are propagated. To ensure that the correct assessment and procedures are completed at each study visit, the data collection program will be programmed to include only the study assessments and procedures relevant to that visit. The data collection program will also require that all questions be answered or refused, and we will build in skip patterns and logic checks for values entered to ensure data quality and completeness. We will closely monitor each step of the specimen collection, transport, storage, and analysis process to ensure that all specimens are continuously accounted for and stored and transported in conditions that will ensure their integrity. The project manager and RA will conduct weekly checks to confirm that the number of specimens collected match the number of assessments completed, and that the number of assessments completed match the number of visits. The research nurse will conduct a weekly check to ensure that the short-term specimen storage conditions are appropriate (e.g., refrigerator and freezer are the correct temperature) and will make adjustments as necessary.

The RA will monitor EMD devices continuously throughout the study to identify those devices that have not been seen by the server in the last week. If after 7 days the device still is not seen at all on the server, the RA will call the participant to see if there are any problems with the device and troubleshoot. The RA will also

conduct an EMD test at each study visit to identify and trouble-shoot any potential problems with the device.

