#### 4.2. Dependent Variables

The dependent variables in this analysis are:

1. EMD measured ART adherence – Number of days EMD is opened from baseline to six-month follow-up (0 to 180 days) among participants in each arm.
2. Biological measures of ART adherence – Number of participants in each arm who are virally suppressed and adherent as measured through biological testing.
3. Self-reported ART adherence – Assessed by a validated three-item ART adherence scale. The three items are: 1) *Days taken* -- number of days the patient missed at least one dose of their medication (number of days, 0-30); 2) *Frequency* -- how often the patient took their medication in the way they were supposed to in the past 30 days (never/rarely/sometimes/usually/almost always/always); and 3) *Rating* – how good a job the patient did in taking their medication in the way they were supposed to in the past 30 days (very poor/poor/fair/good/very good/excellent). Responses were then linearly transformed into a scale of 0 to 100 (higher scores indicate greater adherence). The average score across the three items was calculated to represent overall adherence. Scale reliability among this sample was high (Cronbach's  $\alpha = .90$ ).
4. Uptake of OST – Number of participants who reported they were currently taking OST at the six-month follow-up.

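### The EMD day count has no rule for openings that are not doses, so study-prompted openings can score as adherent days: a small upward bias in adherence, of uncertain sign for the arm difference

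*Protocol*

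**What the plan says.** SAP 4.2 item 1 defines the primary dependent variable as "Number of days EMD is opened from baseline to six-month follow-up (0 to 180 days) among participants in each arm", and SAP 4.5 compares it between arms by t-test. Protocol 4.6.6 gives a monthly version: "EMD-measured adherence will be operationalized as percentage of days/doses for which a device-opening signal was received in the past month". Under both, a day counts because the device was opened, and the same section says: "Pills will be deposited into the EMD device, which will record every time the device is opened".

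The protocol also arranges device handling that is not dosing:

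- **Baseline (4.6.1).** The RA is to "conduct an EMD test to confirm that the device is working properly and is connected with the data server". Section 4.6.6 adds a set-up call to confirm that openings register with date and time.
- **IPI (4.6.3) and 3 months (4.6.4).** The RA runs an EMD "test and will check in with the participant regarding EMD uses and resolve any issues". The device is mailed back at 6 months. Section 5.1 states more broadly that the RA will "conduct an EMD test at each study visit to identify and trouble-shoot any potential problems with the device".
- **Fills (4.6.6).** "The device can store a 30-day supply of medication".
- **Troubleshooting (4.6.6 and 5.1).** The RA calls when the server has not seen the device for 7 days.

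No section of either document flags, logs or removes openings made for these purposes.

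**The concern.** An extra opening on a day when a dose is also taken changes nothing. On a missed day it turns the day into an adherent one. Less adherent participants have more missed days, so each test or set-up opening inflates their count more. That raises the measured level of adherence in both arms and can also distort the difference between them.

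This matters because Protocol 4.7 gives the pilot the job of estimating planning parameters accurately enough to size a later trial. It names mean adherence and the proportion reaching 95% over a month. Those estimates and the between-arm difference would all carry the error.

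**Working it through.** **The plan's own figure.** Protocol 4.6.12 states 80% power with 30 dyads per arm, f = 0.15 and alpha 0.05 in a repeated-measures within-between ANOVA. Take N = 60, m = 4 assessments, and an assumed within-person correlation of 0.5 with sphericity (neither is given). Then lambda = f² × N × m/(1 - rho) = 0.0225 × 60 × 4/0.5 = 10.8 on 3 and 174 df, and power is 78.6%. The stated figure reproduces to within 2 points. It does not depend on how openings are counted.

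**Inputs for the check**

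- Window: 180 days (SAP 4.2).
- Tests: 3, at baseline, IPI and 3 months (Protocol 4.6.1, 4.6.3, 4.6.4). That each involves an opening is an inference.
- Fills: at most about 180/30 = 6, from the 30-day capacity. The documents give no number.
- Adherence levels: assumed, with a true difference of 15 points, or 0.15 × 180 = 27 days.

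**Formula.** If k non-dose openings fall on separate days unrelated to dosing, observed days = 180p + k(1-p). With the same k in both arms, observed difference = true difference × (1 - k/180).

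- Tests only, k = 3: loss 3/180 = 1.7%, so 27 days become 26.55.
- Tests plus six fills for everyone, k = 9: loss 9/180 = 5.0%, so 27 days become 25.65. False days at k = 9 are 6.3 at 30% adherence, 4.5 at 50% and 2.7 at 70%.

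**Fills that follow pill use.** If participants refill only when the pills run out, fills number about 6p, and false days are (3 + 6p)(1-p):

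| Adherence, SOC vs intervention | False days, SOC | False days, intervention | Loss, days | Loss, % of 27 |
|---|---|---|---|---|
| 30% vs 45% | 3.36 | 3.135 | 0.225 | 0.8% |
| 50% vs 65% | 3.00 | 2.415 | 0.585 | 2.2% |
| 80% vs 95% | 1.56 | 0.435 | 1.125 | 4.2% |

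Tests plus fills therefore give roughly 1% to 5%, depending on how fills track adherence.

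**Direction.** Under Protocol 4.6.2 only the intervention arm has three sessions that review EMD data. If each prompted an opening, that arm would gain 3(1-p) days. At p = 0.65 this is 1.05 days, against a loss of 3 × 0.15 = 0.45 days from tests alone at 50% vs 65%. The net bias would be 0.60 days in favour of the intervention.

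**Power.** A simulated t-test used 30 per arm, 15-point differences, beta-binomial days with an assumed precision of 3, and 20,000 runs. At k = 9, power without and with the extra openings was 0.632 and 0.632 (50% vs 65%), 0.681 and 0.678 (60% vs 75%), and 0.787 and 0.786 (70% vs 85%). The spread shrinks along with the difference: in the first case the SOC standard deviation fell from 45.4 to 43.2 days.

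**The 95% cut.** With one daily dose over 30 days, 28/30 = 93.3% fails and 29/30 = 96.7% passes. One non-dose opening on either of two missed days reclassifies the participant. For a single opening on a random day the chance is 2/30 = 6.7%.

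**Troubleshooting.** Adding call-triggered openings that rise with non-adherence to k = 9 gave simulated losses of about 8% to 9% with up to 8 calls, and about 13% to 18% with up to 26 (about 180/7, the ceiling). These counts are assumed.

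**The case against.** The strongest reply is that the openings are inferred. The baseline test is described as checking function and server connection. No section says that a test or a call includes an opening on a day without a dose. This stands in part. The set-up call must confirm that openings register with date and time, which most naturally needs one, but the figures for tests remain conditional.

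A reader might infer that the 7-day call singles out people who are missing doses. Someone taking none would then be credited with about 25 to 28 of 180 days (3 tests plus 22 to 25 call-triggered openings), or 14% to 16%. The documents do not support this. The trigger is a device not seen on the server. Whether a connected but unopened device counts as unseen is not stated, and no opening during the call is mentioned.

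Fills are also weaker evidence than they look. They fall as pill use falls, so they do not add most error in the least adherent, and many may coincide with a dose.

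Finally, the documents call openings a proxy for adherence and carry biological and self-reported measures as separate outcomes. That is fair context, but it supplies no rule for counting openings known not to be doses.

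**Conclusion.** The point holds as a small, correctable bias. The counting rule as written would score some days without a dose as adherent, and nothing in either document removes them. The understatement of the arm difference is about 1.7% for tests alone and roughly 1% to 5% for tests plus fills. Those figures assume that each test involves an opening, that timing is unrelated to dosing, that extra openings are equal in the two arms, and that a true difference exists. With no true difference and equal openings there is no bias between arms.

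Two stronger conclusions are tempting and do not follow. One is that the rule reliably shrinks the arm difference: openings at intervention-only sessions would act the other way, so the sign is not settled. The other is that the trial loses power: the simulated change at k = 9 is well under one point. Losses above 10% need frequent troubleshooting openings, whose number the documents do not give, and are illustrative only.

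**What to change.** In SAP 4.2 item 1, define an adherent day as one with at least one opening that does not match, by date and time, a recorded set-up, visit-test or troubleshooting contact. Report the unfiltered day count alongside as a sensitivity analysis.

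Keep fill openings in the main count. A participant may fill the device and take the dose in one opening, so dropping fills could cost a fully adherent person up to about 6 of 180 days, as much as the error being removed. Examine fills only in a sensitivity analysis, and only if fill times are known. Openings that coincide with intervention sessions can be examined in the same way if session times were kept.

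The SAP describes enrolment and device use in the past tense, so new logging may come too late for this trial. Where contact times were not kept, state that as a limitation, and log them from now on or in the next trial.

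The cost is a short data-cleaning step, slightly lower reported adherence, and the occasional loss of a true dose taken during a test.
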